5.3 SCREEN FAILURES

A subject who has signed a consent form, has been assigned a screening number, but is not treated is classified as a screen failure. Subject number, demographics and reason for screen failure will be recorded.

6 STUDY TREATMENT

6.1 INVESTIGATIONAL PRODUCT DESCRIPTION

PRO 140 is a humanized IgG4,κ monoclonal antibody (mAb) to the chemokine receptor CCR5. PRO 140 is provided at a concentration of 175 mg/mL and is intended for SC route of administration.

Kits will be labeled with a unique identification number. Each kit will contain two vials of PRO 140 for SC injection. One milliliter (1 mL) of PRO 140 solution will be drawn from each vial and loaded into the syringe. A total of 700 mg (175 mg/mL) of PRO 140 is delivered as two (2) mL injections administered subcutaneously on opposite sides of the abdomen. Two study injection kits will be assigned per subject per treatment visit.

Note: Subjects enrolled prior to Protocol v4.0 may still be receiving the original 350mg dose and have the option of increasing their dose to 700mg.

Each vial of the PRO 140 product contains ~1.4 mL antibody at 175mg/ml in a buffer containing 5 mM L-histidine, 15.0 mM glycine, 95 mM sodium chloride, 0.3% (w/v) sorbitol, 0.005% (w/v) polysorbate 20 (Tween 20®), and sterile water for injection, at pH of 5.5.

Note: *1 mL injection will be drawn from 1.4 mL solution in a vial. Remaining 0.4 mL medication will be discarded appropriately from each vial.*

[Table 6-1](#) provide the unit strength, dosing frequency and mode of administration for the study drug.

Table 6-1: Investigational Product - PRO 140

Study Drug	Dosage Form	IP concentration	Dosing Frequency and Amount	Route of Administration
PRO 140	Parenteral solution	175 mg/mL	2 injections of PRO 140 (2 X 2 mL/inj.) per week on opposite sides of abdomen	SC injection

6.2 INVESTIGATIONAL PRODUCT PACKAGING AND LABELING

Study drug will be prepared by Ajinomoto Althea, Inc. and will be packaged, labeled, and shipped by PCI Clinical Services

The contents of each vial are described in [Section 6.1](#). PRO 140 kits will be labeled with information such as: study protocol #; fill volume; concentration; storage condition; a “use as per study protocol” statement; a cautionary statement; sponsor’s name and address; and the kit number.

Below are representative samples of the Investigational Product, FDP individual vial (Figure 6-1), syringe label (Figure 6-2), and kit label (Figure 6-3) designated for use in this clinical protocol. Each kit contains two labeled vials and two syringe labels.

Figure 6-1: Investigational Product - Vial Label

Protocol: PRO 140_CD02	Kit No. 2-xxxxx	Protocol: PRO 140_CD02	Kit No. 2-xxxxx
Subject No. _____		Subject No. _____	
Single use 3 mL vial contains 1.4 mL of PRO 140 (175 mg/mL) solution for subcutaneous injection		Single use 3 mL vial contains 1.4 mL of PRO 140 (175 mg/mL) solution for subcutaneous injection	
Store at 2°C to 8°C (36°F to 46°F)		Store at 2°C to 8°C (36°F to 46°F)	
USE AS PER STUDY PROTOCOL		USE AS PER STUDY PROTOCOL	
Caution: New Drug – Limited by Federal (or United States) Law to Investigational Use		Caution: New Drug – Limited by Federal (or United States) Law to Investigational Use	
CytoDyn Inc., Vancouver, WA, USA		CytoDyn Inc., Vancouver, WA, USA	

Figure 6-2: Investigational Product - Syringe Label

Protocol: PRO 140_CD02	Contents of Kit No. 2-xxxxx
This syringe contains 2 mL PRO 140 (175 mg/mL) solution for subcutaneous injection	
USE AS PER STUDY PROTOCOL	
Caution: New Drug – Limited by Federal (or United States) Law to Investigational Use	
CytoDyn Inc., Vancouver, WA, USA	

Figure 6-3: Investigational Product - Kit Label

Protocol: PRO 140_CD02	Kit No. 2-xxxxx
Site No. _____	Subject No. _____
This kit contains 2 single-use vials	
Each 3 mL vial contains 1.4 mL of PRO 140 (175 mg/mL) solution for subcutaneous injection	
Store at 2°C to 8°C (36°F to 46°F)	
USE AS PER STUDY PROTOCOL	
Caution: New Drug – Limited by Federal (or United States) Law to Investigational Use	
CytoDyn Inc., Vancouver, WA, USA	

Pharmacy manual for PRO140_CD02 study provides the criteria regarding vial acceptance or rejection, as well as instructions for the preparation of the IP syringes to be used to administer drug.

6.3 INVESTIGATIONAL PRODUCT STORAGE

Study drug will be shipped at 2°C to 8°C (refrigerated [36°F to 46°F]) to the investigator's site. Upon receipt at the site, the responsible site staff or pharmacist should verify the integrity of the vials. Study drug should be stored at 2°C to 8°C (refrigerated [36°F to 46°F]). The contents of the vial should appear as a clear to opalescent, colorless to yellow solution; fine translucent particles may be present. This is normal.

The investigator must maintain an accurate record of the shipment, storage, and dispensing of the study drug in a drug accountability log. An accurate record including the date and amount of study drug dispensed to each subject must be available for inspection at any time. A study CRA assigned to monitor the investigational site will review these documents once study drug has been received by the investigational site. Study drug will be accounted for on an ongoing basis during the study.

6.4 INVESTIGATIONAL PRODUCT ADMINISTRATION

Guidelines for dose preparation can be found in the PRO140_CD02 or CD02_OpenLabel Pharmacy Manual.

PRO 140 will be provided to the administering personnel in single-use syringes prepared from vials of study drug stored at 2-8°C at the site pharmacy prior to use. Each of two syringes is filled to deliver 2.0 mL of study drug.

Equivalent volumes of study drug will be administered subcutaneously on opposite sides of the abdomen.

A 25-gauge needle should be used to remove IP from vial and for administration to subjects.

IP should be administered slowly over 15 seconds per mL. IP should not be kept in syringe for longer than 60 minutes.

Following each SC delivery of drug, careful examination will be made to assess the appearance of any study drug Injection Site Reactions (ISRs) as described in [Section 16.3](#).

All doses of study drug will be prepared by either the credentialed pharmacist or qualified medical professional and will be administered as SC injection by a qualified medical professional (MD, DO, PA, LPN, LVN, NP, RN, or CMA if permitted by state law) or self-administered by subjects depending on the study visit week.

Note: It is preferred that the same injection site be used throughout the study. At the same time, it is not recommended to inject the study drug into areas where skin shows signs of a previous injection site reaction. It is advised to change the injection site if any previous injection site reaction remains unresolved. Alternatively, the 700 mg dose may be delivered as four 1mL doses (two SC injections on opposite sides of abdomen) for those that experience discomfort with the 2mL injections (i.e. subjects with low body fat percentages).

6.5 INVESTIGATIONAL PRODUCT RECEIPT AND ACCOUNTABILITY

Study drug must be used in accordance with this protocol and only under the direction of the responsible investigator. The investigational site must maintain complete and accurate records showing receipt and disposition of all study drug, including master records listing the date of receipt, the number and nature of medication units received, and a dispensing record which includes each quantity dispensed, identification of the staff member/subject to whom dispensed, the date of dispensing, the intended study participant, and the identification of the preparer. All used and unused study kits will be retained by the investigational site until drug accountability can be confirmed by study CRA during the monitoring visits. Instructions will be provided by Sponsor regarding final disposition of all study drug in compliance with applicable regulations.

6.6 INVESTIGATIONAL PRODUCT DISPOSITION

All drug supplies are to be used only for this protocol and not for any other purpose. The investigator must not destroy any drug labels or any partially used or unused drug supply until instructed by the Sponsor. At the conclusion of the study and as appropriate during the course of the study, the investigator will return all used and unused drug containers and drug labels to the drug distributor as directed by the Sponsor. A copy of the completed drug disposition form will be sent to CytoDyn, Inc. or to its designee.

7 DESCRIPTION OF PROTOCOL ASSESSMENTS AND PROCEDURES

7.1 INFORMED CONSENT

Written informed consent will be obtained for this study by the Investigator or designee from all subjects before the performance of any protocol-specific procedure. This study will be conducted in accordance with the provisions of the Declaration of Helsinki.

In obtaining and documenting informed consent, the Investigator must comply with applicable regulatory requirements and must adhere to Good Clinical Practice (GCP). The Investigator, or designee, must fully inform subjects of all pertinent aspects of the study. Before informed consent may be obtained, the Investigator, or a person designated by the Investigator, must provide the subject ample time and opportunity to inquire about details of the study and to decide whether or not to participate in the trial. All questions about the trial must be answered to the satisfaction of the subject. Prior to the subject's participation in the trial, the written informed consent must be signed and personally dated by the subject and by the person who conducted the informed consent discussion. Authorization for release of protected health information must also be obtained, as per local policies.

7.2 ASSESSMENT OF ELIGIBILITY

During the Screening Phase and at TE1 Visit (prior to treatment administration), the Investigator must assess a subject's continued suitability and eligibility for the trial. The Inclusion and Exclusion criteria of this Protocol are described in [Sections 3.3.1](#) and [3.3.2](#). If the subject is not suitable or eligible for the trial then the subject will be a screen failure.

7.3 DEMOGRAPHIC INFORMATION

For the purposes of this study, demographic information will include:

- Dates of ICF signature
- Date of birth
- Gender
- Race (American Indian/Alaskan Native, Asian, Black/African American, Native Hawaiian/Pacific Islander, Caucasian, or other)
- Ethnicity (Hispanic/Latino or Not Hispanic/Latino)

7.4 MEDICAL HISTORY

Medical history obtained within PRO140_CD02 or CD02_OpenLabel study will be brought forward.

Events that emerge after first treatment (TE1) will be recorded as AE under this protocol.

7.5 HIV HISTORY

HIV history obtained within PRO140_CD02 or CD02_OpenLabel study will be brought forward.

7.6 PRIOR / CONCOMITANT MEDICATIONS AND NON-STUDY TREATMENTS

A complete record of current antiretroviral therapies will be recorded in the source documents and on the appropriate page of the eCRF.

In addition to this, all other medications and therapies administered or taken by the subject throughout the study will be recorded. Subjects must be questioned at each study visit concerning any new medications or changes in current medications including over-the-counter medication.

For each medication and non-study treatment, the following will be documented:

- Medication/treatment name (generic name may be used if trade name is unknown)
- Dose, unit, and frequency of dosing (individual dosages, not total daily dose).
 - **Note:** *Each new dose of medication should be recorded as a separate entry, with the exception of medications that are given on a sliding scale. For these, it is acceptable to enter the range of the dosage, including the start and stop dates for which the specified dosage range was used.*
- Route of dosing
- Indication for use
- The start date
- The stop date (if medication/therapy is not ongoing)

Please refer to Exclusion Criteria ([Section 3.3.2](#)) for a list of prohibited treatments and/or procedures. All other medications that are appropriate for the care of the subject may be prescribed. If concomitant medications are started during the study, the indication for the concomitant medication should be considered an AE.

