1.6 RISKS / BENEFITS ASSESSMENT

1.6.1 RISKS/DISCOMFORT TO SUBJECTS AND PRECAUTIONS TO MINIMIZE RISK

1.6.1.1 Risks associated with virologic failure

Subjects participating in the PRO140_CD02 or CD02 Open Label study will continue to receive study treatment (PRO 140 700mg SC injection) in addition to Optimized Background Therapy (OBT). Addition of study treatment (PRO 140 700mg SC injection) to OBT may not be effective for continued suppression of viral load for all subjects.

Note: Investigator will construct a new HAART regimen should viral rebound occur, where HIV-1 viral load meets virologic failure criteria.

Note: Subjects enrolled prior to Protocol v4.0 may still be receiving the original 350mg dose and

have the option of increasing their dose to 700mg.

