3.3 ELIGIBILITY CRITERIA

3.3.1 Inclusion Criteria

[figure not shown]
Subjects must meet all of the following criteria to be included in the study:

1. Subjects who have completed 24 weeks of treatment in PRO 140_CD 02 or CD02_OpenLabel study, and Investigator believes subject requires continued access to PRO 140 in order to continue deriving clinical benefit and maintain HIV-1 viral suppression.
2. HIV-1 RNA <50 at T23 Visit in PRO140_CD02 or CD02_Open Label study
3. Both male and female patients and their partners of childbearing potential must agree to use 2 medically accepted methods of contraception (e.g., barrier contraceptives [male condom, female condom, or diaphragm with a spermicidal gel], hormonal contraceptives [implants, injectables, combination oral contraceptives, transdermal patches, or contraceptive rings], and intrauterine devices) during the course of the study (excluding women who are not of childbearing potential and men who have been sterilized). Females of childbearing potential must have a negative serum pregnancy test at Screening visit and negative urine pregnancy test prior to receiving the first dose of study drug.
4. Willing and able to participate in all aspects of the study, including use of SC medication, completion of subjective evaluations, attendance at scheduled clinic visits, and compliance with all protocol requirements as evidenced by providing written informed consent.

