7.11.10 CCR5 Receptor Occupancy

- To assess the number CCR5 receptors on patients' CD4 cell surface. Of those CCR5 receptors, the test will also assess the number and percentage of CCR5 receptors that are covered by PRO 140.
- Frequency of testing: This assessment will be performed up to 5 times at different treatment visits. Blood will be taken prior to PRO 140 injection (trough sample) and 24-48 hours (peak sample) after the PRO 140 injection to check for CCR5 occupancy, and correlative analysis will be performed with PRO 140 PK concentration and HIV-1 RNA levels.

All laboratory reports will be reviewed by the Investigator.

Post-treatment abnormal results that are considered by the Investigator to be clinically significant will be recorded as adverse events. If the Investigator judges it necessary, testing may be repeated in order to make the determination of clinical significance. Validated, quality-controlled laboratory data will be transferred to the main database for analyses.

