9.1 ADVERSE EVENT

An adverse event (AE) is defined as any unfavorable or unintended sign, symptom, or disease that occurs or is reported by the subject to have occurred, or a worsening of a pre-existing condition. An AE may or may not be related to the study treatment.

AEs will be elicited through direct questioning and subject reports. Any abnormalities in visit evaluations, physical examination findings or laboratory results that the Investigator believes are clinically significant to the research subject and that occurred after initiation of the first study treatment will be reported as AEs. Abnormal findings that are NOT clinically significant (NCS) should not be recorded as an AE.

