7.2.4.1 Adverse Events

Adverse events will be classified by system organ class and preferred term (PT) according to the most recent MedDRA dictionary.

Since this is an extension of the PRO 140_CD 02 study, all adverse events (AE) that captured in this study will be considered as Treatment Emergent Adverse Events (TEAEs). The following TEAE summaries will be provided, using frequency counts and percentages:

- Overall (i.e., regardless of severity or relationship to treatment)
- By severity grade (mild, moderate, severe, life threatening or death)
- By relationship to study treatment

In addition, separate summaries of SAEs, and AEs resulting in discontinuation of study treatment will be presented.

Unless otherwise specified, at each level of subject summarization, a subject will be counted only once. If there is more than one occurrence of an event, the event of the worst severity or the worst-case relationship category will be summarized.

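### Protocol 7.6 turns the indication of every newly started concomitant medication into an adverse event, which is broader than the AE definition in Section 9.1 and inflates the TEAE tables

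*Protocol*

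**What the plan says.** Protocol 7.6 has sites ask at each visit about new or changed medications, including over-the-counter products, and record the indication and dates of each. It ends with this rule: "If concomitant medications are started during the study, the indication for the concomitant medication should be considered an AE". No qualification follows.

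Protocol 9.1 defines an AE as "any unfavorable or unintended sign, symptom, or disease that occurs or is reported by the subject to have occurred". A further clause covers conditions that the subject already had: "or a worsening of a pre-existing condition". The section adds a limit: "Abnormal findings that are NOT clinically significant (NCS) should not be recorded as an AE".

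Protocol 9.1.1 starts AE reporting at TE1. It requires a grade, a causality, an impact on study treatment and an outcome for every AE.

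Protocol 8.7.5.1 defines TEAEs by onset on or after first treatment. SAP 7.2.4.1 has no onset condition: "all adverse events (AE) that captured in this study will be considered as Treatment Emergent Adverse Events (TEAEs". The SAP then tabulates TEAEs overall, by severity grade and by relationship. At each level of summary a subject counts once, at the worst severity or relationship.

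**The concern.** Section 9.1 asks whether something bad happened to the subject. The last sentence of 7.6 asks only whether a medication was started. The two tests agree for most medications, because most are started for a symptom or a disease. They part when the reason for starting is preventive, elective or long-standing.

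In those cases a site following 7.6 has to open an AE record and grade something like immunization or contraception for severity and causality. A site following 9.1 would record only the medication. With up to 30 centers, similar subjects could be reported differently. The study has a single arm, so no comparator carries the same excess. Treatment is open-ended, which gives each subject a long time in which to start such a medication.

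**Working it through.** The plan gives no figure on this point, so there is none to reproduce. The check sets the passages side by side and then sizes one affected subject.

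**Step 1. Does 7.6 go further than 9.1?**

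| Reason for starting a medication after TE1 | AE under 7.6, read literally | AE under 9.1 |
|---|---|---|
| Vaccination | Yes | No: no sign, symptom, disease or worsening |
| Prophylaxis | Yes | No, for the same reason |
| Hormonal contraceptive, newly started | Yes | No |
| Stable condition already in the medical history | Yes | No: nothing new and nothing worse |
| New or worsened condition | Yes | Yes |

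The documents mention neither vaccination nor prophylaxis as medication indications. These two rows follow from the wording of 7.6 alone.

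The contraception row is narrow. Inclusion criterion 3 in Protocol 3.3.1 says that subjects and partners "must agree to use 2 medically accepted methods of contraception", but barrier methods and intrauterine devices are listed as well as hormonal ones. A barrier method is not a medication, and a method carried over from the parent study is not newly started. Only a hormonal method begun after TE1 fits.

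**Step 2. Does anything exempt these cases?** No passage in either document exempts preventive, elective or stable pre-existing indications. Nor can the verb be softened to a prompt to think about it, since 9.1 uses the same verb form as a recording instruction in "Abnormal findings that are NOT clinically significant (NCS) should not be recorded as an AE".

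**Step 3. Does the analysis filter them out?** The onset condition in Protocol 8.7.5.1 could remove the stable-condition case, provided the site enters the true onset date and not the medication start date. It would not remove a vaccination, whose only natural date falls after TE1. The SAP rule applies no onset condition, so it removes neither.

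**Step 4. Size.** Inputs: maximum enrollment n = 50 (Protocol synopsis); each subject counted once (SAP 7.2.4.1).

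- Change in the any-TEAE rate per affected subject with no other TEAE: 1/n = 1/50 = 0.02, or 2 percentage points. It is larger if fewer than 50 enroll.
- Change in the any-TEAE rate per affected subject who has another TEAE: 0. The record can still add 1/50 to a system organ class or preferred term row in which that subject has no other event.
- Number of affected subjects: not given and not derivable. The total inflation therefore cannot be calculated.

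**Step 5. Which outputs are exposed?** The measures listed in Protocol 8.2 include Grade 3 or 4 AEs, serious AEs, treatment-related AEs leading to discontinuation, and injection site reactions. A preventive or elective indication would rarely qualify for any of these. That is a judgement, not a figure from the documents. The exposure lies in the overall, severity and relationship TEAE tables.

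**The case against.** The strongest reply is that sites will read 7.6 together with the rest of the protocol. The opening of Section 9 makes the investigator responsible for events that meet the AE definition. Section 7.4 treats as AEs the events that emerge after TE1, and 9.1.1 starts reporting there. This gives a sensible site grounds for ignoring the literal rule, and divergent reporting between sites is a possibility rather than something shown. None of these passages qualifies the 7.6 sentence, however, and a site that obeys it is following the protocol.

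The second reply is that little depends on it. The overall TEAE rate is not a listed measure, and the safety analysis is descriptive. In CD01, 29 of 43 subjects (67%) had an AE with up to 12 weeks of treatment. In a longer study, few subjects may have a preventive start as their only event. This stands, and it limits the effect on the any-TEAE rate. It limits the effect on individual event rows less.

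A reader might go further and infer that 7.6 also manufactures AEs from virologic failure, because "Investigator will construct a new HAART regimen should viral rebound occur" and PRO 140 then stops. The documents do not support that:

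- Section 7.6 records antiretrovirals separately from all other medications. SAP 7.1.5 and 7.1.6 also treat antiretroviral therapy and background therapy apart, so it is not established that the new regimen falls under the rule.
- Subjects enter suppressed. A confirmed rebound can itself be a worsening under 9.1, or a clinically significant laboratory result under the closing text of 7.11.10: "Post-treatment abnormal results that are considered by the Investigator to be clinically significant will be recorded as adverse events". There may well be a real AE behind it.
- Virologic failure is a stopping reason in its own right (Protocol 5.2.1 and 8.1), and discontinuation reasons are reported under disposition (8.7.1). The listed discontinuation measure also requires the AE to be treatment-related.

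**Conclusion.** The point holds for preventive indications, newly started hormonal contraception and drugs newly started for stable pre-existing conditions. It is a stated rule that gives a wrong result when followed, and the SAP passes that result into the TEAE tables unfiltered.

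The size is 2 percentage points on the any-TEAE rate for each affected subject with no other TEAE, assuming all 50 places are filled. The total is unknown. The overall, severity and relationship tables are affected, while the listed Grade 3-4, serious and treatment-related-discontinuation measures probably change little. The conclusion assumes that sites apply 7.6 as written. It does not extend to virologic failure, and no figure can be attached to that route without assuming a failure rate that the documents do not give.

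**What to change.** Replace the last sentence of Protocol 7.6 with:

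> When a concomitant medication is started, the site checks whether its indication meets the AE definition in Section 9.1 with onset or worsening on or after TE1, and records an AE only if it does. Preventive, contraceptive and stable pre-existing indications are recorded as the reason for the medication and are not AEs by themselves.

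This keeps the useful part of the rule, which is that a new medication prompts a search for an unreported event. It also brings the recorded AEs back in line with the onset condition in Protocol 8.7.5.1, so the SAP's equation of AE with TEAE does no harm for new records.

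For data already collected, flag AE records whose only basis is such an indication, and show the TEAE tables with and without them. Virologic-failure records should not be removed in this step.

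The cost is one protocol sentence, one flag in the AE dataset and a second run of the TEAE tables. The small downside is that sites must judge each indication, which Section 9.1 already asks of them.
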